We propose a three-site, RCT conducted at the Atlanta (lead site), Birmingham and Richmond VA medical centers to establish non-inferiority of pelvic floor muscle exercise-based behavioral therapy compared to drug therapy for urinary symptoms in adults with PD. Groups will be stratified by OAB symptom severity, PD motor symptom severity, gender, and site. We will randomize 90 participants in order to complete the study in 80 participants, assuming 85% power and a non-inferiority margin for the OAB symptom score of 15% at 12-weeks. **The primary outcome measure will be urinary symptom severity as measured by the ICIQ-OAB symptom score^{32,33}** collected at 3 time points during the study: baseline, 6 weeks, and 12 weeks. PFME-based behavioral therapy will occur over 3 visits conducted during the first 6 weeks as was performed in the BETTER2 PD study. Participants in the drug therapy group will also have 3 visits during the first 6 weeks in order to individually titrate solifenacin drug therapy according to a validated symptom scale. Solifenacin has been selected because this bladder-selective anticholinergic drug (less risk of cognitive side effects) is the only drug with published evidence of potential efficacy in PD³⁴. At baseline, randomized participants will undergo a brief neuropsychological battery adapted from our current study to assess cognitive factors that may predict a preferred treatment strategy. At the 12-week assessment, the brief neuropsychological battery and MDS-UPDRS will be repeated in order to assess any change associated with treatment allocation. Follow-up visits will occur at weeks 4 and 8 to ascertain side effects and assess treatment adherence.

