6. The **Geriatric Depression Scale-Short Form** is a 15-question assessment that has been validated in older adults and is recommended as a screening test for depression in adults with PD⁴³.
7. The **Self-Efficacy for Managing Chronic Disease** questionnaire is a 6-item questionnaire developed through the Stanford Patient Education Research Center. It covers several domains that are common across many chronic diseases, symptom control, role function, emotional functioning and communicating with physicians⁴⁴.
8. **Physical Exam and Laboratory testing**
 - Urinalysis (for all participants) and pregnancy test (for women of child-bearing age). If bacteriuria is suggested by screening urinalysis⁴⁵, a culture will be sent and bacteriuria (>100K colony forming units) will be eradicated by a 7-day antibiotic course with permission/notification sent to their primary care provider. Participants will be re-assessed for UI following treatment. Participants with unexplained, persistent hematuria will be referred for an appropriate evaluation.
 - HgbA1c if the participant is diabetic and has not had an HgbA1c in the 3 months prior to enrollment.
 - Basic metabolic panel if the participant has not had an assessment in the 6 months prior to enrollment.

Enrollment and Neuropsychological Assessment:

One week later, potential participants will return for visit two. Study staff will review the completed bladder diary, questionnaires, and PVR and will determine if the participant qualifies for the study. Once enrolled, participants will undergo a brief neuropsychological battery and a motor task of procedural learning. These tests will be administered by a research assistant so that the principal investigator is blinded to baseline performance on the SRTT and cognitive function. The selected tests correspond with the battery piloted in the PI's current Rehab R&D CDA-2 study and are manageable for participants with PD. These assessments will

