Randomization: At the second visit, eligible participants will be randomized to one of two groups: treatment with PFME-based behavioral therapy or solifenacin drug therapy. Participants will be stratified by site, gender, UI severity (< or \geq a score of 9 on the ICIQ-OAB), and PD motor symptom severity (MDS-UPDRS < 33 on the part 3 motor score)⁵⁹. Participants will be randomized through computer-generated block randomization in groups of six. Based on preliminary data showing these cut points approximate the means among our randomized participants, we do not anticipate four stratification variables will present a challenge to recruitment. While participants will not be blinded to treatment group, the interventionist will be blinded to the participant's performance on the neuropsychological tests and SRTT performance.

Data Management: Participants' assessment data will be kept in a locked cabinet behind a locked door at each site of the Birmingham/Atlanta GRECC and the Richmond PADRECC. Bladder diaries will be scored by a research assistant who is blinded to the assigned treatment group. Data from the Birmingham and Richmond sites will be uploaded to a secure VA server in the form of PDF documents scanned on a VA device behind the VA firewall. Deidentified data will be entered and verified in Redcap by research staff at the Atlanta site, which will ensure accuracy of the data. A standard form will be used to record the date and reason for all

exclusions and dropouts, and these data will also be entered into the master database. Four times per year the PI will meet with the Atlanta-based data manager to review accrual, data entry, and eligibility criteria and examine the database for outliers or database entry errors at each site. The Redcap database will then be converted and data analyses will be completed in SAS 9.4 (SAS Institute, Cary, NC). Additional details regarding confidentiality of patient data are included in the Human Subjects plan.

Specific Aim #1: Using a RCT, determine non-inferiority of pelvic floor muscle exercise-based behavioral therapy versus drug therapy for urinary symptoms in PD.

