Regardless of whether behavioral therapy proves to be inferior or non-inferior to drug therapy, understanding the potential association of drug therapy with cognition or PD motor symptom severity are important factors for patients and providers to determine next steps for treatment⁶⁹.

Measures: Participants in both groups will complete a baseline and 12-week neuropsychological battery as previously described including the MoCA test, SRTT, CERAD Word List subtest, Nonverbal/Spatial Reminding Test, Wisconsin Card Sort Test, and the Subject Ordered Pointing task. We will use the Anticholinergic Risk Scale⁴⁷ to calculate an overall anticholinergic drug score for participants in both groups based on medications listed at the randomization visit as a potential effect modifier. The MDS-UPDRS will be repeated at the 12-week visit. Thus, the behavioral therapy group will serve as a control group to assess the potential impact of solifenacin drug therapy on domain-specific cognitive function and PD motor symptom severity.

Data Analysis: [The analysis for aim 2b will generate data informing how central cognitive control of sensory integration and motor function are involved in the response to drug therapy.] Baseline and 12-week post-randomization cognitive tests will be evaluated using paired t-tests to assess for change within the drug group and two-sample t-tests for differences across groups (the behavioral therapy group will serve as a control for this analysis). Because cognitive impairment in PD most often manifests as impaired executive function, we will focus on tests of this domain, such as the Wisconsin Card Sort Test or the Subject Ordered Pointing Task in our evaluation of impact on cognition. The clock-draw test, as a component of the MoCA, is another assessment of executive function that is often performed in clinical practice. If changes are noted on domain-specific assessments of the neuropsychological battery, we will also examine correlation with clock draw scores obtained through the MoCA test. The Anticholinergic Risk Scale will be assessed based upon medications at randomization. The Anticholinergic Risk Scale score will be included in a multivariable model including baseline characteristics associated with changes in cognitive function in bivariable analyses.

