To assess the potential impact on motor symptoms, we will assess the change in the motor symptom subscale of the MDS-UPDRS (part 3 score). Similar to the cognitive testing, baseline and 12-week post-randomization assessments will be evaluated using paired t-tests to assess for change within the drug group and two-sample t-tests for difference across groups, with the behavioral therapy group serving as a control for this analysis. Previous research suggests an increase in the MDS-UPDRS part 3 score of 4.6 points is associated with clinically relevant decline in motor function⁷⁰.

Visit Schedule

Visit 1: Baseline (One phone/telehealth session and one in-person session)

Explanation of study procedures and consent to be a participant

Interview: Demographics, continence and medical history, MoCA, LSA, GDS

Physical: Height, weight, vital signs, cardiac, pulmonary, and abdominal exam, genital and rectal exam, basic neurologic exam, MDS-UPDRS, determination of post-void residual by bladder ultrasound

Laboratory Examination: Urinalysis and BMP and HgbA1c if indicated

Education: How to complete bladder diary, handout take-home questionnaires (ICIQ-OAB and OAB-QOL)

Visit 2 (Part 1) : Randomization

Interview: Collect and review 7-day bladder diary, ICIQ questionnaires

Physical: Vital signs; review laboratory results; determination of post-void residual by bladder ultrasound if not conducted at first visit;

Procedure: **Randomization (Behavioral Therapy or Drug Therapy)**

Behavioral Therapy	Drug Therapy

Visit 2 (Part 2): Behavioral Therapy Randomization
 
Procedure: Neuropsychological battery, SRTT, Pelvic floor muscle exercise training
 
Education: specific behavioral techniques for constipation, modification of fluid intake or timed voiding
	
Visit 2 (Part 2) : Drug Therapy Randomization
 
Procedure: Neuropsychological battery, SRTT
 
Education: Medication

Visit 3: Behavioral Therapy (2 weeks)
 
Interview: Review PFME record, address new problems, reinforce practice at home and verbal feedback regarding muscle control
 
Education: Urge suppression strategy, management of stress-related urine loss (if applicable)
	
Visit 3: Drug Therapy (2 weeks)
 
Interview: Medication Management, Medication Side Effects
 
Education: Medication & Bladder Diary & Forms (to return at Visit 5)

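### As scheduled, the Visit 2 neuropsychological battery and SRTT follow open-label randomization, so this cognitive baseline is a post-allocation measure, mainly a risk to Aim 2b

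*Combined protocol and SAP*

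**What the plan says.** In the Visit Schedule, the last procedure of Visit 2 Part 1 is "Randomization (Behavioral Therapy or Drug Therapy". Part 2 follows in two columns, one per arm. The behavioral column lists "Neuropsychological battery, SRTT, Pelvic floor muscle exercise training". The other column, headed "Visit 2 (Part 2) : Drug Therapy Randomization", lists the battery and SRTT together with medication education.

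Research Design and Methods agrees with that order: "At baseline, randomized participants will undergo a brief neuropsychological battery adapted from our current study".

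Two other sections bear on timing without settling it. Enrollment and Neuropsychological Assessment says "Once enrolled, participants will undergo a brief neuropsychological battery and a motor task of procedural learning". The Randomization section says "At the second visit, eligible participants will be randomized to one of two groups".

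On blinding, the Randomization section states "While participants will not be blinded to treatment group". A research assistant gives the tests so that the principal investigator does not see the scores, and the interventionist is also kept from them. Only the bladder-diary scorer is stated to be blind to treatment group (Data Management).

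On use, the Aim 2b Measures paragraph says "the behavioral therapy group will serve as a control group to assess the potential impact of solifenacin drug therapy". Aim 2a uses SRTT and Wisconsin Card Sort performance at baseline as predictors.

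**The concern.** Randomization balances what is measured before it. A score taken once the participant, and possibly the tester, knows the arm no longer has that protection. Each session lasts about 75 minutes and includes memory, working-memory and reaction-time tasks, on which expectation and effort can matter.

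Aim 2b asks whether solifenacin worsens executive function, with these scores as the starting point. If knowing the arm moves one group's starting scores, the difference enters any change from baseline and can look like a drug effect on cognition, or hide one. A participant who withdraws between allocation and testing also has no baseline, and such losses could differ by arm.

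**Working it through.** **Order of procedures.** The plan states no figure on this point, so the check is a comparison of sections.

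| Section | What it implies about order |
|---|---|
| Visit Schedule, Visit 2 Parts 1 and 2 | Randomize, then battery and SRTT, in both arms |
| Research Design and Methods | Battery is taken by people already randomized |
| Enrollment and Neuropsychological Assessment | After enrollment; relation to allocation not stated |
| Table 7 | Baseline, Visit 1 or 2; no order given |

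Two sections put the battery after allocation and none puts it before.

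**Which Aim 2 baselines are affected.**
- Affected: SRTT, CERAD Word List, Nonverbal/Spatial Selective Reminding, Wisconsin Card Sorting and Subject Ordered Pointing.
- Not affected: MoCA, which is in the Visit 1 interview.
- Not affected: MDS-UPDRS part 3. The Visit Schedule puts it at Visit 1 and Baseline Assessments at the second visit, but as a stratification factor it must be known before allocation.
- Not affected: the Aim 1 ICIQ-OAB baseline, collected before randomization.

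**Illustration of size.** The only input from the documents is 40 per arm (80 completers in two groups). The assumptions are:
- baseline and 12-week scores each have SD 1;
- their correlation is ρ = 0.7;
- there is no true drug effect;
- one arm's baseline is shifted by d = 0.2 SD, and a fraction k of that shift is still present at week 12.

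*Between-group t-test on change, two-sided 5%, 78 df.*
- SD of change = √(2(1 − ρ)) = √0.6 = 0.775.
- Standard error = 0.775 × √(2/40) = 0.173.
- Bias = d(1 − k); noncentrality = bias / 0.173; critical t = 1.991.

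| Shift persisting to week 12 | Bias (SD) | Noncentrality | Rejection rate |
|---|---|---|---|
| None (k = 0) | 0.20 | 1.155 | 21% |
| Half (k = 0.5) | 0.10 | 0.577 | 9% |
| All (k = 1) | 0 | 0 | 5% |

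Sensitivity for a baseline-only shift: at d = 0.1 and 0.3 the rates are 9% and 40%. At d = 0.2 with ρ from 0.5 to 0.8 the range is 14% to 29%.

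*Baseline-adjusted comparison, d = 0.2.* Residual SD = √(1 − 0.49) = 0.714, and bias = d(k − ρ). With k = 0 the bias is 0.14 in absolute value and the test rejects about 14% of the time. With k = 1 the bias is 0.06 and it rejects about 7%. Adjustment reduces the problem but does not remove it.

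*Paired t-test within the drug group, if that is the shifted arm, 39 df.* Standard error = 0.775/√40 = 0.1225. With d = 0.2 and k = 0, noncentrality = 1.633 and the test rejects about 36% of the time. With k = 1 it returns to 5%.

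**The case against.** The case against is substantial, and much of it stands.

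- **The shift may persist.** The same unblinded participants repeat the battery at 12 weeks. A shift that lasts cancels in the change score, and a clean baseline would then expose a contaminated 12-week score: at 0.2 SD, 21% rejection on change and 24% with baseline adjustment. This stands against quoting a single error rate. It does not justify relying on one contaminated measurement to cancel another.
- **The between-group test may not be on change.** Aim 2b specifies paired tests of change within the drug group and two-sample tests across groups, without saying that the latter use change. If they compare 12-week scores, the baseline does not enter. This stands; the paired test is exposed either way.
- **Aim 2a is little affected.** Its detailed analyses are all within the behavioral arm, where everyone has the same assignment. A uniform shift changes no correlation or slope. This stands.
- **Scoring dampens general effort.** SRTT is a within-person difference between random and sequenced blocks, with the sequence unknown to the participant. Perseverative errors are residualized on total errors. This stands for those two measures as a reduction of the risk.
- **The Enrollment section comes before the Randomization section,** so testing first may be intended. But it does not say so, and the visit-by-visit schedule says otherwise.

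A reader might go further and infer that treatment has already affected the baseline. The documents do not support that: the battery is listed before pelvic floor training, and no text has solifenacin taken before testing. Nor do they support the inference that every Aim 2 baseline is compromised, given where MoCA and MDS-UPDRS part 3 fall.

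**Conclusion.** The point holds for the Visit 2 battery and SRTT. As scheduled, they are given after open-label allocation, with no stated blinding of the tester to arm. The main exposure is Aim 2b: the paired test within the drug group, and the between-group test if it is run on change. Loss between allocation and testing is a secondary risk. For Aim 2a the concern is minor. The Aim 1 comparison is untouched.

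The order of procedures is clear from the text, but the bias is not established: neither its size nor its direction is known. The between-group range of 5% to 21% at a 0.2 SD shift shows how far the answer depends on an unverifiable assumption about persistence. It should not be read as the trial's actual error rate. The point is worth correcting because analysis can only partly repair a baseline that allocation has influenced, whereas reordering prevents that influence.

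**What to change.** Move the battery and SRTT to Visit 2 Part 1, after eligibility is confirmed and before the allocation is drawn, and remove them from the arm-specific Part 2 columns. Change the Research Design and Methods sentence so that the baseline battery is taken by eligible participants before randomization, and state the same order in the Enrollment section.

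The visit, staff and tests stay the same. The one cost is that an occasional person will be tested and then not randomized, which should be rare because eligibility is already settled in Part 1.

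Reordering does not address the open-label 12-week test. The plan should therefore also state whether the tester is blind to arm at that visit.

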Power Analysis: The power analysis is informed by the ICIQ-OAB symptom score reduction observed in the BETTUR PD and BETTUR2 studies of behavioral therapy for urinary symptoms in PD. Based upon the bladder diary-derived UI frequency data (consistent measure used in both behavioral and drug trials), the effect of behavioral therapy and drug therapy to reduce UI frequency is similar. The ICIQ-OAB symptom score range is 0-16, with higher scores indicating worse symptoms. A score \geq 7 would indicate clinically significant OAB symptoms (urgency, frequency, urgency UI, nocturia) occurring on average at least *sometimes*. In our previous studies, we have observed a 2-3 point reduction in the symptom score, which represents a 12%-19% reduction from baseline^{24,64}. The minimally clinically important difference for the ICIQ-OAB is defined as a statistically significant reduction in the symptom score that is accompanied by a reduction in bother and improvement in OAB-specific QOL. Because the observed reduction **\geq 2 points** represents a statistically and clinically meaningful difference, we propose a non-inferiority margin of 15%. Thus, we will randomize 90 participants in order to complete the interventions in 80 participants, which assumes 85% power and a non-inferiority margin on the OAB symptom score of 15% at 12-weeks post-randomization. **Table 6 indicates that the proposed sample size will permit an assessment of non-inferiority within a range of potential non-inferiority margins that correspond to outcome assessments in our pilot studies.**

Standard Deviation of 12 week ICIQ-OAB Symptom Score	Margin of Non-Inferiority Between Groups at 12 weeks (Assumes OAB Symptom Score at baseline of = 8.1)				
	10%	12.5%	15%	20%	
	1.0	23	16	11	7
2.0	89	59	40	24	
3.0	198	131	88	52	

Table 7: Summary Outcome Assessments

Outcome Assessment	Baseline Visit 1/Visit 2	2 weeks Visit 3	4 weeks Visit 4	6 weeks Visit 5	8 weeks Visit 6	12 weeks Visit 7
ICIQ-OAB	X			X		X
7-day Bladder Diary (drug)	X			X		X
7-day Bladder Diary (behavioral)	X	X		X		X
7-day PFME Record (behavioral)		X				
ICIQ-OAB QOL	X			X		X
Benefit & Satisfaction				X		X
Life Space Assessment	X			X		X
Self Efficacy for Chronic Disease Management	X					X
Patient Global Symptom Control Score				X		X
Adverse Event checklist	X	X	X	X	X	X
Adherence Questionnaire		X		X		X
Neuropsychological battery	X					X
MDS-UPDRS	X					X

Data Analysis:

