Self-assessed adherence to exercise or drug therapy will be assessed through questionnaires (both groups) and with exercise records or pill counts depending on group allocation. Data will be calculated as medians (and inter-quartile range), and compared using Kruskal-Wallis test for continuous variables or chi-square test (Fisher's exact when expected cell counts were <5) for categorical variables. Adverse event questionnaires will be administered at each in-clinic or phone visit after treatment allocation. The number of times a specific side effect is reported after the baseline assessment will be summed and presented as a continuous variable. Comparisons between groups of the proportion of participants reporting specific side effects will be performed by Fisher's exact test.

[Specific Aim #2 (mechanistic aim): Determine if domain-specific cognitive function impacts the response to exercise-based behavioral therapy or drug therapy for urinary symptoms.

Aim 2a: Do higher baseline motor skill learning capacity and executive function scores predict better outcomes in the exercise-based behavioral therapy versus drug therapy group?

Rationale: In spite of the potential for cognitive impairment, which occurs in up to 75% of PD patients within 10 years of diagnosis²⁹, some PD patients demonstrate evidence of neuroplasticity and benefit from learning motor skills as demonstrated through functional imaging studies^{30,31}. Understanding whether baseline domain-specific cognitive function is associated with successful implementation of behavioral therapy among adults with PD is important to understand the central control of bladder function and identify new targets to augment rehabilitation therapy in the setting of a neurodegenerative disease. While participants with significant cognitive impairment (MoCA < 18) will be excluded, this exclusion criterion will not eliminate participants with mild cognitive impairment. The range of MoCA scores among current completers of the BETTUR2 PD study (n=26) is 18 to 29 (mean=24.6 ± 2.9). Among the 11 participants randomized to behavioral therapy in the BETTUR2 PD study who had a MoCA score between 18-26 (includes the screening cutpoint for mild cognitive impairment in PD³⁷), the median reduction in weekly UI frequency eight weeks after randomization was 88% (IQR 42%-100%), suggesting that even mild cognitive impairment does not interfere with learning a behavioral therapy intervention.

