Human Subjects Involvement and Characteristics: Men and women with PD recruited from the Atlanta, Birmingham, Richmond, and Philadelphia VAMCs as well as in the surrounding community. We propose randomizing 90 participants to either exercise-based behavioral therapy or drug therapy with Solifenacain. In order to complete the study in 80 participants, we anticipated having to screen approximately 180 PD patients to identify those with clinically significant OAB symptoms, and enroll approximately 45 participants in each group. These estimates are based on our experiences in the BETTUR PD and BETTUR2 pilot studies. In the BETTUR PD study, 33 individuals were screened to enroll 20 participants. Of the 20 participants who were enrolled, 17 completed the study demonstrating a 15% drop out rate once enrolled. To date, in the BETTUR2 study, we have screened 107 individuals to randomize 51 participants and have had 6 participants drop out (11.7% rate).

During FY16, 541 unique Veterans with PD were served by the Atlanta VA and surrounding CBOCs. For the BETTUR PD pilot, 14 of the 32 screened subjects were recruited from the Atlanta VA after mailing letters to 360 Veterans identified with a diagnosis of PD in the Metro Atlanta area in FY08. Recruitment was extended to a university-based movement disorders clinic to achieve the intended sample size of 20 enrolled subjects. For the BETTUR2 study, of the 65 persons who have undergone screening procedures thus far, 25 were Veterans and 40 were recruited from university-based movement disorders clinics in Atlanta and Birmingham in order to maximize the team's ability to recruit the intended sample size. Thus, we propose to recruit both Veterans and non-Veterans for the proposed study from the outset. The university affiliates in Atlanta (Emory), Birmingham (University of Alabama at Birmingham), Richmond (Virginia Commonwealth University), Philadelphia (University of Pennsylvania) all have active movement disorders programs, which enhance the overall resources available to the study.

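### Randomizing 90 to complete 80 allows 11.1% loss, slightly less than either pilot dropout rate given as its basis, so the plan has no reserve for 80 completers

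*Combined protocol and SAP*

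**What the plan says.** The opening paragraph of Research Design and Methods states: "We will randomize 90 participants in order to complete the study in 80 participants". The Power Analysis section and the sample-size paragraph under Human Subjects repeat the numbers in terms of the interventions: "we will randomize 90 participants in order to complete the interventions in 80 participants". Human Subjects Involvement and Characteristics adds that the sites will "enroll approximately 45 participants in each group" and attributes these estimates to the BETTUR PD and BETTUR2 pilots.

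That section then gives the pilot experience. For BETTUR PD, of 20 enrolled, "17 completed the study demonstrating a 15% drop out rate once enrolled". For BETTUR2, "To date, in the BETTUR2 study, we have screened 107 individuals to randomize 51 participants" and "have had 6 participants drop out (11.7% rate"). The Potential Risks section also says discontinuation was at most 15%. No planning dropout rate is stated for this trial.

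The primary non-inferiority test (Data Analysis, Primary Outcome for Aim 1) is a two-sample t-test on the 12-week ICIQ-OAB symptom score, with a 15% margin, an SD of 2.0 and one-sided alpha of 0.025.

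**The concern.** The allowance for loss is meant to follow from the two pilots, yet the loss it permits is lower than the rate in either. The lower pilot rate is also an interim count over everyone randomized. Anyone still in follow-up sits in the denominator and could still drop out.

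The number matters because the t-test uses week-12 scores and the plan describes no handling of missing scores for that test. The participants with a week-12 score are therefore the analysed sample. The planned table cell needs exactly 40 per arm, so any shortfall comes straight off the stated power.

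**Working it through.** **Inputs**
- 90 randomized, 80 completers, about 45 per group: Research Design and Methods, Power Analysis, Human Subjects.
- Pilot losses 3/20 and 6/51: Human Subjects Involvement and Characteristics.
- Baseline score 8.1 and margin 15%: Power Analysis table. Margin = 0.15 × 8.1 = 1.215 points.
- SD 2.0 and one-sided alpha 0.025: Primary Outcome for Aim 1.
- My assumptions: true difference zero, equal arms, completer means a participant with a week-12 score.

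**Step 1: reproduce the plan's figures.** With n per arm, the noncentrality is 1.215 / (2.0 × √(2/n)) on 2n − 2 degrees of freedom. For 85% power at one-sided 0.05, this needs n = 40, which matches the table and gives 80 in total. At the stated one-sided 0.025 it needs n = 50 (49 by normal approximation). Power is therefore shown on both bases below.

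**Step 2: allowed loss against quoted loss.**
- Allowed: (90 − 80)/90 = 11.11%
- BETTUR2: 6/51 = 11.76% (printed as 11.7%), 0.65 points higher
- BETTUR PD: 3/20 = 15.0%, 3.89 points higher
- Pooled: (6 + 3)/(51 + 20) = 9/71 = 12.68%, 1.57 points higher

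**Step 3: consequences.** Expected completers = 90 × (1 − d). Number to randomize to expect 80 = 80/(1 − d), rounded up. The chance of at least 80 completers is binomial with 90 trials. Power uses half the expected completers in each arm.

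| Loss d | Expected completers | Per arm | Chance of ≥ 80 | Randomize to expect 80 | Power, one-sided 0.05 | Power, one-sided 0.025 |
|---|---|---|---|---|---|---|
| 11.11% (plan) | 80.0 | 40.0 | 58% | 90 | 85.3% | 76.5% |
| 11.76% (6/51) | 79.4 | 39.7 | 51% | 91 | 85.0% | 76.2% |
| 12.68% (9/71) | 78.6 | 39.3 | 40% | 92 | 84.7% | 75.8% |
| 15.0% (3/20) | 76.5 | 38.25 | 19% | 95 | 83.8% | 74.6% |

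The largest power loss is 85.3 − 83.8 = 1.5 points at 0.05, or 76.5 − 74.6 = 1.9 points at 0.025.

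**Step 4: precision of the pilot rates.** Exact 95% intervals are 4.4% to 23.9% for 6/51, 3.2% to 37.9% for 3/20, and 6.0% to 22.7% for 9/71. All include 11.1%.

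**The case against.** The best defence is that 90 is a rounded planning figure. At the larger pilot's rate it falls short by 0.6 of a participant, 91 would be needed instead of 90, and the chance of reaching 80 is still about one half. A clear shortfall appears only at 15%, from a 20-person pilot. The pilot rates are too imprecise to rule out 11.1%, and the statement of at most 15% in Potential Risks is compatible with it. The Drug Intervention section also lets people who stop solifenacin stay for data collection, so stopping treatment need not mean a missing week-12 score. All of this stands, and it limits the point to a lack of reserve. It does not remove the mismatch: neither cited pilot rate, nor the two pooled, yields 80 from 90.

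A reader might infer a much higher loss in two ways, and the documents support neither.
- **Joining two BETTUR2 counts.** The Aim 2a Rationale mentions "current completers of the BETTUR2 PD study (n=26"). Setting these 26 beside the 6 dropouts would suggest 6 lost among 32 resolved participants. The two counts are not dated, and Human Subjects gives both 107 and 65 as numbers screened in BETTUR2, so the figures appear to come from different dates.
- **Extrapolating from eight to 12 weeks.** The Aim 2a Rationale reports that "the median reduction in weekly UI frequency eight weeks after randomization was 88"%. That is the timing of an outcome. The documents do not say that dropouts were counted only to week eight, nor do they give any hazard over time.

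**Conclusion.** The concern holds as a modest inconsistency. The allowed loss of 11.1% sits slightly below both pilot rates named as its basis, and the plan has no reserve for 80 completers. The protocol's own rates give about 76 to 79 expected completers, and the power cost is under 2 points on either alpha.

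A reader might go further and conclude that 80 completers will not be reached. The documents do not show that: at 6/51 the expectation is 79.4.

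The result rests on treating the pilot rates as applicable here. Three gaps limit that. The BETTUR2 count is interim, and the number still in follow-up is not given. The period over which its dropouts were counted is not given. The Power Analysis describes both pilots as studies of behavioral therapy, so neither rate speaks directly to retention on solifenacin.

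The roughly 9-point gap between the two power columns (85.3% against 76.5% with 80 completers) is a separate and larger matter. It comes from the table's 40 per arm matching one-sided 0.05 while the analysis states 0.025. Restating completers does not resolve it.

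**What to change.** 1. In Research Design and Methods, Power Analysis, and both the recruitment and sample-size paragraphs under Human Subjects, restate the expected completers from 90 as about 76 to 79 (about 78 to 79 at the pooled rate), and name the rates used: 6/51, 9/71 and 3/20.
2. Quote power over that range at the stated alpha. For a margin of 1.215, an SD of 2.0 and no true difference, this is 74.6% to 76.2% at one-sided 0.025. If the alpha is reconciled differently, recompute on that basis.
3. Update the BETTUR2 dropout rate using only participants whose follow-up has ended, with a data cut-off date and the follow-up length, and revise the range if it changes.
4. Say whether a completer is someone who finishes the intervention or someone with a week-12 score, since the text uses both the study and the interventions as the thing completed.

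The cost is a change of wording and one recalculation. The stated completers and power become slightly less favourable, and no extra enrolment is needed.
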